**e) Instruments:**

Subjects will be rated weekly on PSQI, Insomnia severity index, CGI and MADRS. They will be requested to keep daily sleep diaries and wear actigraphy devices throughout the three week period of study.

**Insomnia severity Rating Index:** This instrument has been shown to be a reliable and valid to detect cases of insomnia in the population and is sensitive to treatment response in clinical population. It is a 7-item self-report questionnaire assessing the nature, severity, and impact of insomnia. The usual recall period is the “last month” and the dimensions evaluated are: severity of sleep onset, sleep maintenance, and early morning awakening problems, sleep dissatisfaction, interference of sleep difficulties with daytime functioning, noticeability of sleep problems by others, and distress caused by the sleep difficulties. A 5-point Likert scale is used to rate each item (e.g., 0 = no problem; 4 = very severe problem), yielding a total score ranging from 0 to 28. The total score is interpreted as follows: absence of insomnia (0-7); sub-threshold insomnia (8-14); moderate insomnia (15-21); and severe insomnia (22-28). Three versions are available—patient, clinician, and significant others—but the present paper focuses on the patient version only. Previous studies have reported adequate psychometric properties for both the English and French versions.

**PSQI:** Pittsburgh Sleep Quality Index is 10-item scale evaluating various domains of subjectively reported sleep. The score can be between 0-21. A score of less than 5 indicates good sleep quality whereas a score greater than 5 indicates poor sleep quality.

**CGI:** Clinical Global Impression is an easily administered clinician rating scale assessing overall clinical impression.

**MADRS:** Montgomery Asberg Depression Rating Scale is a 10-item questionnaire used by clinicians to rate the severity of depression.

**Mini Mental State Exam (MMSE):** assesses potential impairment in cognition (thinking)

**Sleep diary:** Sleep diaries are used both in research and clinical practice in the treatment of insomnia. Diaries will be completed daily by patients, reporting bedtime, wake up time, awakenings and various other daytime activities.

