#### **Potential problems:**

A potential problem could be worsening of insomnia during TMS treatment. We will monitor subjects weekly and rate their insomnia and depressive symptoms. A MADRS score above 9 would necessitate a clinical interview to assess for depression. If subjects are found to have clinical depression, they will be released from the study and offered treatment in our outpatient clinic. We will study about 25 patients to get 20 completers. Patients with various sleep disorders including insomnia are referred to our sleep disorders' clinic. We see about 70 new patients a month. About 15% of these patients are found to have insomnia. These patients are of all ranges. We expect to enroll the requisite number of patients in the study period. We will hold regular study related meetings with all study personnel to document progress.

If a seizure or other medical condition arises during the course of TMS treatment, the study physicians will ensure appropriate medical evaluation.

**Data Analysis and Statistical Methods:** We shall compare baseline to post treatment via a one-sample t-test, using a two-sided P-value <0.05 to declare significance. The Total Pittsburgh Sleep Quality Index (PSQI) will be the primary outcome variables. Other outcomes will be analyzed in a similar manner, but the study is powered strictly around PSQI. Significant findings on secondary variables will not be considered as definitive.

**Power for a sample size of N=20 completing subjects:** Based on results from the study of a large cohort of poor sleeping subjects had a cross sectional mean PSQI of 11.6 (SD=2.5). Conservatively assuming that the repeated measures correlation is between 0.70 and 0.80 (Repeat measures assume 50-65% of the variation), the study has 80% power to detect 0.66 standard deviations of the paired difference. This translates to sensitivity to a 1.04 to 1.28 unit

difference in pre to post mean (9%-11% change in the mean PQSI). Final sample size will be 25 subjects to allow for a dropout rate of 20%. Every attempt will be made to collect the PSQI on both days, whether the subject is compliant or not. We shall approximate intent-to-treat as closely as possible, including attempts to get non-compliers to do the post-test and carrying the last observation forward.

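### The only analysis text that reaches the MMSE is a t-test of mean change, which is a poor way to show cognitive decline in a few patients; a per-patient listing and count should be added

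*Combined protocol and SAP*

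**What the plan says.** Section e) Instruments gives the MMSE one purpose: it "assesses potential impairment in cognition (thinking"). The Schedule of Events places it on Days 1, 7, 14 and 21. The sentence in the same section that lists the weekly ratings leaves it out: "Subjects will be rated weekly on PSQI, Insomnia severity index, CGI and MADRS".

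The paragraph Data Analysis and Statistical Methods (under Potential problems) sets the test: "We shall compare baseline to post treatment via a one-sample t-test, using a two-sided P-value <0.05 to declare significance". It then adds: "Other outcomes will be analyzed in a similar manner, but the study is powered strictly around PSQI". The MMSE is not named there, nor in either specific aim or hypothesis. The paragraph on secondary endpoints defines responders by a reduction of at least 30%. That concerns improvement in sleep and does not cover the MMSE.

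No MMSE cut-off, definition of decline, listing or count of decliners is given. The MADRS, by contrast, has a patient-level rule: a score above 9 leads to a clinical interview. Adverse events are recorded in every column of the schedule, but no MMSE score is linked to them.

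**The concern.** An instrument that looks for impairment asks whether any patient got worse. A t-test of the mean asks whether the group moved. When a few patients fall and the rest do not, the unchanged majority dilutes the mean, and the falls themselves inflate the SD in the denominator. A larger fall therefore does little to make the test more sensitive.

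The test also uses only two values per patient, baseline and post-treatment. For a completer, a drop on Day 7 or 14 that recovers by Day 21 never enters it, although the score was collected.

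At stake is what the pilot can say about cognition. Its results are meant to support a larger randomised trial. A non-significant mean change could be carried forward as reassurance while the trial's own records show individual declines.

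**Working it through.** **1. The plan's own power figure.** The documents give no MMSE power figure. The stated one is for PSQI: "Power for a sample size of N=20 completing subjects" and "the study has 80% power to detect 0.66 standard deviations of the paired difference".
- Noncentral-t power with n = 20, effect 0.66 SD and two-sided 0.05 is 79.95%, so the 80% reproduces.
- SD of the difference = 2.5 × √(2(1 − ρ)) = 1.94 at ρ = 0.70 and 1.58 at ρ = 0.80. Multiplied by 0.66, this gives 1.28 and 1.04 units, as stated.
- 20 / (1 − 0.20) = 25 enrolled, as stated.

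The PSQI calculation is sound. It says nothing about falls in a few patients on another scale.

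**2. Closed form, with no MMSE figures needed.** Let k of n patients fall by d points and the rest not change.
- Mean change = −kd/n.
- Variance s² = k d²(n − k) / [n(n − 1)].
- t = mean / (s/√n) = −√[k(n − 1)/(n − k)]. The size of the fall, d, cancels.

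For n = 25 (24 df, critical value 2.064):

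| Patients who fall | t | two-sided p |
|---|---|---|
| 1 | −√(24/24) = −1.00 | 0.33 |
| 2 | −√(48/23) = −1.44 | 0.16 |
| 3 | −√(72/22) = −1.81 | 0.083 |
| 4 | −√(96/21) = −2.14 | 0.043 |

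Significance first appears at four patients.

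**3. With measurement noise (assumed inputs).** The documents give no SD of MMSE change and no size of a marked fall. Both are assumptions: SD 1 to 1.5 points, falls of 4 to 5 points, changes in whole points, 100,000 simulated trials per case. A trial misses the falls if the two-sided 0.05 test shows no significant decline. Miss rates for n = 25 and a 5-point fall, by the average change in the other patients:

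| Average change in others | SD | 1 faller | 2 fallers | 3 fallers |
|---|---|---|---|---|
| 0 | 1.0 | 96.2% | 91.9% | 81.9% |
| 0 | 1.5 | 95.5% | 91.5% | 84.0% |
| −0.1 | 1.0 | 90.6% | 83.0% | 68.0% |
| −0.1 | 1.5 | 91.7% | 85.6% | 75.2% |
| −0.25 | 1.0 | 73.8% | 61.0% | 41.9% |
| −0.25 | 1.5 | 82.1% | 72.2% | 58.9% |

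- With falls of 4 to 5 points and no average change in the others, the range over 1 to 3 fallers is about 82–96%.
- With 20 completers the rates are much the same: a significant decline in 3.2–4.4%, 7.4–8.7% and 15.2–18.3% of trials for 1, 2 and 3 fallers.
- Widening the assumptions to SD 0.5–2.5 and falls of 3–10 points, with no average change in the others, still gives miss rates above 80%.
- An average repeat-testing gain of 0.3 points leaves a significant decline in at most 2.7% of trials.

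**4. What a count would show.** The exact 95% CI for 2/25 (8%) is 1.0–26.0%. For 0/25 the upper limit is 1 − 0.025^(1/25) = 13.7%.

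**5. Noise in that count.** Assume change SD 1.5, independent visit errors and no true change. Counting each patient's largest fall over the three follow-up visits flags on average 2.8 of 25 patients at 3 points or more (at least one in 95% of trials), and 0.65 at 4 points or more (at least one in 48%). With SD 1 and a 4-point cut-off it is about 0.02. At Day 21 alone with SD 1.5, whole-point scoring gives 25 × Φ(−2.5/1.5) = 1.2 at 3 points and 25 × Φ(−3.5/1.5) = 0.24 at 4 points.

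**The case against.** The strongest reply is that the plan never says the MMSE will be t-tested. The outcomes it names are sleep measures, so the general clause could be meant for those alone, with the MMSE serving as clinical monitoring. That stands as a limit on wording: a reader might infer that the plan chose this test for the MMSE or made it a safety endpoint, and the documents say neither. It does not remove the point. On that narrower reading the MMSE has no stated analysis at all, and the same addition is needed.

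Second, patient-level safeguards exist. Physicians monitor for adverse events, and patients can be withdrawn for an adverse event or a new clinical situation. This stands in part: an overt case may well be noticed, and it would be wrong to infer that cognitive decline would pass unseen. But nothing ties an MMSE score to those safeguards.

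Third, the sponsor nowhere says it will report a non-significant change as no cognitive effect. That is correct, and no such intention should be inferred. The plan does say that significant secondary findings are not definitive, but this does not guard against over-reading a non-significant one.

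Fourth, the miss rate depends on the other patients not drifting down, and a small general decline is a plausible pattern of harm. This stands fully, as the −0.1 and −0.25 rows show. Finally, a count of largest falls in an uncontrolled study picks up noise. This also stands, and it shapes the fix.

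**Conclusion.** The point holds as a modest one about the analysis of an ancillary measure. The only stated analysis that reaches the MMSE, through a general clause, is a test of mean change that is ill suited to showing impairment in individuals and leaves out the interim scores of completers.

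The firmest result is the closed form: with 25 patients and no change in the others, identical falls in 1 to 3 patients cannot reach p < 0.05, whatever their size. The 82–96% range rests on an assumed change SD of 1–1.5 points, falls of 4–5 points and no average change in the other patients. For three fallers it drops to about 67–77% if the others drift down by 0.1 point, and lower still at 0.25. A reader might take a miss rate above 80% as a property of this trial. The documents do not support that, because they give no MMSE figures and the rate depends on that condition.

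**What to change.** In Data Analysis and Statistical Methods, add a short MMSE paragraph:
- Report the mean MMSE change as descriptive only, outside the outcomes tested for significance.
- List each patient's change from Day 1 at Days 7, 14 and 21.
- Report the number of patients whose score falls by at least a cut-off fixed before analysis, both at any visit and at Day 21, with exact 95% CIs, beside the adverse events.
- State that a non-significant mean change will not be taken as absence of a cognitive effect.
- Set the cut-off above expected test-retest noise, and say that without a control arm the count is descriptive and cannot separate noise from harm.

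The sentence on weekly ratings in section e) Instruments should also be reconciled with the schedule, which includes the MMSE. Any clinical action on an MMSE fall is for the sponsor to define.

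The cost is one listing and a simple count from data already collected, with no new visits or procedures. The downside is that some flagged falls will be noise.

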#### **Potential problems:**

A potential problem could be worsening of insomnia during TMS treatment. We will monitor subjects weekly and rate their insomnia and depressive symptoms. A MADRS score above 9 would necessitate a clinical interview to assess for depression. If subjects are found to have clinical depression, they will be released from the study and offered treatment in our outpatient clinic. We will study about 25 patients to get 20 completers. Patients with various sleep disorders including insomnia are referred to our sleep disorders' clinic. We see about 70 new patients a month. About 15% of these patients are found to have insomnia. These patients are of all ranges. We expect to enroll the requisite number of patients in the study period. We will hold regular study related meetings with all study personnel to document progress.

If a seizure or other medical condition arises during the course of TMS treatment, the study physicians will ensure appropriate medical evaluation.

**Data Analysis and Statistical Methods:** We shall compare baseline to post treatment via a one-sample t-test, using a two-sided P-value <0.05 to declare significance. The Total Pittsburgh Sleep Quality Index (PSQI) will be the primary outcome variables. Other outcomes will be analyzed in a similar manner, but the study is powered strictly around PSQI. Significant findings on secondary variables will not be considered as definitive.

**Power for a sample size of N=20 completing subjects:** Based on results from the study of a large cohort of poor sleeping subjects had a cross sectional mean PSQI of 11.6 (SD=2.5). Conservatively assuming that the repeated measures correlation is between 0.70 and 0.80 (Repeat measures assume 50-65% of the variation), the study has 80% power to detect 0.66 standard deviations of the paired difference. This translates to sensitivity to a 1.04 to 1.28 unit

difference in pre to post mean (9%-11% change in the mean PQSI). Final sample size will be 25 subjects to allow for a dropout rate of 20%. Every attempt will be made to collect the PSQI on both days, whether the subject is compliant or not. We shall approximate intent-to-treat as closely as possible, including attempts to get non-compliers to do the post-test and carrying the last observation forward.

Other sleep parameters will be evaluated as secondary endpoints, and a descriptive analysis of responders (reduction by at least 30%) to non-responders will help identify subgroups to be targeted in future. We will analyze the differences in outcome between subjective (PSQI scores, ISI, SOL on PSQI and sleep diaries, TST on sleep diaries and PSQI) and objective measures (actigraphy computed SOL, TST and WASO) between the baseline and end of treatment. We will also analyze the predictive value of insomnia symptoms and severity in predicting treatment efficacy of TMS as a secondary variable. Given the small sample size, we may see differences/trends in this regard that will need to be studied in larger studies. Last Observation Carry Forward (LOCF) strategy will be used to study dropouts. We will also contact those subjects that drop out to ask for the reason for drop-out.

### ***Design Decisions and Limitations***

The sample size is small but necessarily constrained by the cost of the SenStar Treatment Links. We chose to conduct an open label efficacy and feasibility trial based on our clinical and research experience indicating that 1) insomnia is associated with cortical hyper-arousal and low dose TMS is inhibitory. This design will assess effectiveness of the low dose regimen while probing for a possible mechanism for effectiveness. We have proposed recruiting subjects between the ages of 21 and 65. While this is a very broad age range, cortical hyper-arousal is implicated regardless of age. Effectively, the incidence of insomnia increases with age so that our sample is more likely to include middle-aged and older adults.

### **Conflict of Interest:**

None

